1.4 STUDY DESIGN

1.4.1 Design Summary

The study is designed as a within-subjects single-blinded crossover study. Fourteen smokers of tobacco cigarettes and cannabis will switch between three conditions, namely: (a) vaping cannabis leaf, (b) vaping tobacco containing nicotine and (c) vaping a combination of cannabis leaf and tobacco containing nicotine. All participants will vape each product with the PAX loose-leaf vaporizer.

PAX vaporizers will be purchased by the study team. The cannabis leaf will be obtained through the National Institute on Drug Abuse Drug Supply Program. The tobacco containing nicotine, used in conditions (b) and (c) will come from commercially available Marlboro brand cigarettes. The same amount of cannabis or tobacco will be used in all conditions.

The study will be conducted during three outpatient visits separated by at least 48 hours. The order of treatment (cannabis leaf, tobacco with nicotine, cannabis leaf & tobacco with nicotine) will be counterbalanced between subjects. Subjects will be blinded to the content of the vaporizer on the study day but will be told during screening that they will vape cannabis alone, tobacco alone, and cannabis plus tobacco with nicotine.

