1.42 Number of Subjects

A total of 14 subjects will be enrolled in this study over a period of about 6 months. The anticipated accrual rate is approximately 2-4 subjects per month.

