1.6.2 Subject assignment to conditions

	1	2	3	4	5	6	7	8	9	10	11	12	13	14
Study Day 1	C	T	C+T	C	T	C+T	C	T	C+T	C	T	C+T	C	T
Study Day 2	T	C+T	C	T	C+T	C	T	C+T	C	T	C+T	C	T	C+T
Study Day 3	C+T	C	T	C+T	C	T	C+T	C	T	C+T	C	T	C+T	C

*Where, C is cannabis leaf; T is tobacco cigarettes; C+T is cannabis leaf + tobacco cigarettes. Order of enrolled subjects will be counterbalanced; order is assigned at admission.

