3.2.5 Forms for Data Collection

During recruitment participants will complete the following below.

1. REDCAP Online Screen
2. Phone Screen Evaluation

At Screening participants will complete the following below.

The Screening Packet consists of the following forms:

3. Personal Data Form

4. Demographic Information
5. Nicotine/Tobacco Product Use Form
6. Electronic Cigarette or E-Cigarette History
7. Penn State E-Cigarette Dependence Index
8. E-Cigarette Use Assessment
9. Smoking History Screening Form [Cigarettes]
10. Alcohol Use
11. Non-medical Drug Use
12. Medical History
13. Physiological Assessment Form
14. Center for Epidemiological Studies Depression Scale (CES-D)
15. Fagerström Test for Nicotine Dependence (FTND)

Participants will also complete:

16. THC History Questionnaire
17. Severity of Dependence Scale (SDS)

The outpatient questionnaires consist of the following forms:

1. Marijuana Cravings Questionnaire- Short Form (MCQ-SF)
2. Positive Affect Negative Affect Schedule (PANAS)
3. Minnesota Nicotine Withdrawal Scale (MNWS)
4. Modified Cigarette Evaluation Questionnaire (mCEQ)
5. Drug Effect Questionnaire (DEQ-5)

3.3 **ORIENTATION**

Subjects will be asked to come back to the UCSF Tobacco Research Center for an Orientation Visit at least 48 hours before Study Day 1. This visit will take approximately 30 - 45 minutes. The following will happen during the Orientation Visit:

- A urine sample will be collected and saved.
- Participants will be asked to not use marijuana or marijuana-containing products for 12-hours prior to each study visit.
- Participants will be asked to not use tobacco cigarettes or nicotine-containing products for 12-hours prior to each study visit.
- Participants will be asked to not use any recreational drugs from that point until the study is completed.
- Study procedures will be reviewed with the participants, who will do practice sessions of outpatient questionnaires and gas trap procedure.

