6.3 DATA ANALYSIS

The study is not hypothesis-driven but will provide valuable data to guide future research as well as provide needed data on THC delivery and effects from vaping. Variables of interest include amount of THC inhaled, amount exhaled, and amount retained; pharmacokinetic parameters for THC, 11-OH-THC, and nicotine, the psychoactive compounds; heart rate and blood pressure change; and subjective effects.

Delivered and Retained Doses: Delivered THC and nicotine doses are estimated as the change in e-cigarette weight \times concentration of THC or nicotine in e-liquid. The amount of THC or nicotine systemically retained is estimated as delivered dose minus amount in gas traps.

THC, 11-OH-THC, and Nicotine Pharmacokinetics: Pharmacokinetic parameters will be estimated from blood THC and 11-OH-THC and plasma nicotine concentrations using Phoenix WinNonlin 6.3 (Pharsight Corporation, Mountain View, CA). Time to max concentration (T_{max}), max concentration (C_{max}), and area under the blood/plasma concentration-time curves (AUC) will be estimated using a non-compartmental model and trapezoidal rule. C_{max} , and $AUC_{0 \rightarrow \infty}$ will be adjusted for baseline nicotine levels.

Averages and 95% confidence intervals will be computed by e-liquid type (THC only or

THC+nicotine). Although this study is not hypothesis-driven, we will use mixed model analysis of variance (ANOVA) to assess differences in these variables between e-liquids type. Models will include sex as a covariate.

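### Section 6.3 names no study-day term for a three-day crossover; adding one is a cheap, modest gain in precision if outcomes drift between days

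*Combined protocol and SAP*

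**What the plan says.** Section 1.4.1 describes the design: "The study is designed as a within-subjects single-blinded crossover study", and "The study will be conducted during three outpatient visits separated by at least 48 hours". On order it says that "The order of treatment (cannabis leaf, tobacco with nicotine, cannabis leaf & tobacco with nicotine) will be counterbalanced between subjects". Section 1.42 sets the size: "A total of 14 subjects will be enrolled in this study over a period of about 6 months".

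Section 1.6.2 gives the assignment table. Its first row reads "Study Day 1 C T C+T C T C+T C T C+T C T C+T C T", and the note beneath adds: "Order of enrolled subjects will be counterbalanced; order is assigned at admission". Only three cyclic orders appear.

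Section 6.3 is the whole analysis plan. It promises averages with 95% intervals by product type, worded as two types (THC alone, and THC with nicotine), and a mixed-model ANOVA to compare types. The only other model term it names is sex: "Models will include sex as a covariate". Study day, period and order do not appear as model terms anywhere. The section calls the study not hypothesis-driven and gives no alpha, power, effect size or SD.

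**The concern.** The design goes to the trouble of rotating conditions over three days, but the analysis as worded does not use the day. In a crossover, balancing over periods keeps a day effect largely out of the treatment contrasts. It does not keep it out of the error term. Unless day is modelled, a common shift between days is treated as unexplained within-person noise, and every interval widens.

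Sex cannot do this job, because it takes the same value on all three days of a given person.

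Some drift is plausible on the documents. At the Orientation visit, participants are described as those "who will do practice sessions of outpatient questionnaires and gas trap procedure"; no session with the vaporizer is listed. Eligibility requires weekly inhaled cannabis by smoking and/or vaping, so experience with this device is not required. Day 1 may therefore be a participant's first prompted 5-second puff with a 10-second hold, and it is the first study day with a catheter and 11 blood samples. Participants are also told at screening which three products they will receive, so by Day 3 some may guess the last one by elimination, which could move subjective ratings. At stake is precision in a study of 14 people whose stated purpose is to supply data for later research.

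**Working it through.** **Inputs.** Orders come from the table in 1.6.2. The within-person residual SD is set to 1 (σ), because the documents give none. Drift is an assumption and is shown as a range. D is the total linear change from Day 1 to Day 3, so d = D/2 per day. The plan states no sample-size calculation, so there is no figure of its own to reproduce.

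**Step 1: count the orders.** C, T, C+T: 5 participants. T, C+T, C: 5. C+T, C, T: 4. Counts on Days 1/2/3:

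| Condition | Days 1/2/3 | Mean day |
|---|---|---|
| C | 5/4/5 | 28/14 = 2.000 |
| T | 5/5/4 | 27/14 = 1.929 |
| C+T | 4/5/5 | 29/14 = 2.071 |

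**Step 2: leak into contrasts without a day term.** Subtracting the counts gives:
- C+T minus C: (Day 2 − Day 1)/14
- C+T minus T: (Day 3 − Day 1)/14
- C minus T: (Day 3 − Day 2)/14

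With D = 1σ these are 0.036σ, 0.071σ and 0.036σ. With 12 or 15 participants in equal orders they are exactly zero. If two participants in the third order were lost (5/5/2), the mean days would be C+T 27/12 = 2.25 and T 21/12 = 1.75. The C+T minus T leak would then be 0.5d, or 25% of the Day 1 to Day 3 drift.

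**Step 3: error inflation, all three conditions modelled.** Error df are 42 − 14 − 2 = 26. Each person contributes d²(1 + 0 + 1) = 2d², so 28d² in total. The part absorbed by condition is 14 × (0.0714² + 0 + 0.0714²)d² = 0.143d². The expected error mean square is therefore 1 + (27.857/26)d² = 1 + 1.071d². The contrast variance is 2/14 = 0.1429. The 95% half-width without drift is 2.056 × √0.1429 = 0.777σ.

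With a 2-df day term, df are 24 and the contrast variance is 0.1436 (+0.5%). The half-width is 2.064 × √0.1436 = 0.782σ whatever the drift.

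| D | Mean square | SE factor | Half-width, no day term | With day term |
|---|---|---|---|---|
| 0 | 1.000 | 1.00 | 0.777 | 0.782 |
| 0.5σ | 1.067 | 1.03 | 0.803 | 0.782 |
| 1σ | 1.268 | 1.13 | 0.875 | 0.782 |
| 2σ | 2.071 | 1.44 | 1.118 | 0.782 |

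At D = 0.25σ the two half-widths are practically equal (0.783 and 0.782).

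The linear shape is not essential. A shift s confined to Day 1 contributes (4/9 + 1/9 + 1/9)s² = 0.667s² per person. Over 14 people that is 9.33s², less 0.05s² absorbed by condition. The mean square is then 1 + 0.357s², so at s = 1σ the SE factor is √1.357 = 1.16.

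**Step 4: the two-condition comparison that 6.3 words.** Error df are 13, falling to 11 with the day term. With no drift the half-width goes from 2.160 × √0.1429 = 0.817σ to 2.201 × √0.1444 = 0.837σ, which is 2.4% wider. For C against C+T the mean square is 1 + 1.113d²; for T against C+T it is 1 + 0.989d². The term breaks even at D of about 0.42σ and 0.45σ respectively. At D = 1σ the SE factor is 1.13 and 1.12.

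**Step 5: simulation (C+T minus C, true difference 1σ, all three conditions, 20,000 trials per setting).** Power is 71% to 72% with or without the term at D = 0.5σ. At D = 1σ it is 66% without and about 71% with. At D = 2σ it is about 47% without and 72% with. Coverage without the term is about 97% at D = 1σ and 99% at D = 2σ, so the error is on the conservative side.

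**Step 6: sex.** In random-intercept fits on complete data, adding sex changed the condition contrast by less than 1e-14 and its SE by less than 1e-5. With three Day 3 visits missing, the contrast moved by about 0.008σ on average and 0.04σ at most.

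**The case against.** The case against is substantial, and much of it stands.

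- **Drift size.** No document gives one. Noticeable harm needs a total drift of about 1 within-person SD; at 0.5 SD power is unchanged. This stands, and it limits the claim.
- **Same-day baselines.** Section 3.4.1(c) takes heart rate, temperature and catecholamines before vaping on every study day, and 6.3 analyses heart-rate change. A constant day-level shift cancels there, so catheter anxiety on Day 1 is a weak argument for that outcome. Only a drift in the response itself would remain. This stands. Delivered and retained dose, THC and 11-OH-THC kinetics, and subjective effects have no change from a same-day baseline specified in 6.3. The baseline adjustment for nicotine would not remove a drift in the amount inhaled.
- **Practice.** Puffs are fixed and voice-prompted, participants inhale cannabis at least weekly, and the absence of device practice at Orientation is read from silence. That makes drift plausible but not shown.
- **Cost.** For the two-condition wording the price is 2 of 13 error df, not 2 of 26. This stands, and both costs are given.
- **A descriptive study.** With no planned power, a missed 1-SD difference is not a failure against a stated target. True, but 6.3 still promises 95% intervals and comparisons between products, and needlessly wide results serve neither.

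A reader might infer that omitting the day term biases the product comparisons. The table does not support that: with all 14 complete the leak is at most 1/14 of a between-day difference, and coverage is above nominal. Nor is the sex covariate an error; 6.3 does not say it is there to sharpen contrasts. And 6.3 does not exclude a day term. It simply names none.

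**Conclusion.** The point holds as a cheap improvement. As worded, 6.3 would put any day-to-day drift into the residual, and the one covariate it names cannot take it out. The consequence is a conservative loss of precision: about 3%, 13% or 44% on the standard error for an assumed total linear drift of 0.5, 1 or 2 within-person SD, and none worth recovering below about 0.25 SD (0.4 to 0.5 SD for two conditions). The leak into contrasts is minor with complete data and becomes material only if dismissals or dropouts unbalance the orders.

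These sizes rest on an assumed drift, an assumed common residual SD and 14 complete participants. The concern applies mainly to delivered dose, pharmacokinetic and subjective outcomes. It would be wrong to conclude that the planned analysis produces false findings. It would also be wrong to conclude that a day term deals with carry-over: in the three cyclic orders each condition is only ever preceded by the same other one (T by C, C+T by T, C by C+T), and that is a separate matter.

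**What to change.** In section 6.3, specify a linear mixed model with fixed effects for condition, study day (1, 2, 3, as a factor) and sex, and a random participant effect. Report the condition contrasts with 95% intervals from that model.

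The cost is a line of text and 2 error degrees of freedom. If there is no drift, the interval half-width goes from 0.777σ to 0.782σ when all three conditions are modelled together (26 to 24 df), or from 0.817σ to 0.837σ, about 2%, in a two-condition comparison (13 to 11 df). Fitting all three conditions in one model, where the outcome exists for all three, keeps the cost at the lower figure. No new data are needed: study day is already part of the sample label in section 1.6.1.

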7 DUTIES AND RESPONSIBILITIES OF STAFF

7.1 PRINCIPAL INVESTIGATOR

The Principal Investigator is responsible for study design and oversight of implementation, data analysis, and manuscript preparation.

7.2 Study Doctor

The Study Doctor will hold privileges at the CTSI Ward 5B, and will be on call for any serious events that may occur with study participants. They will also be a resource for reviewing medical history, medications, eligibility, or any questions that may pertain to participant eligibility and safety. In some cases the Study Doctor role may be filled by the Study Principal Investigator, [name].

7.2 CO-INVESTIGATORS

The co-principal investigators are responsible for study design and oversight of implementation, data analysis, and manuscript preparation, with the assistance of the Principal Investigator.

7.3 PROJECT MANAGER

The Project Manager is responsible for overall functioning of study coordination with CHR protocols; monitoring of study budget and coordination with departmental administrative personnel; supervision of research associates; management of clinic facilities.

7.4 CLINICAL RESEARCH COORDINATOR

The CRC will oversee study logistics including logging specimens, chart reviews, protocol review, consenting, Screening Visit procedures, scheduling, and orientation procedures.

8 STUDY MANAGEMENT

8.1 PRE-STUDY DOCUMENTATION

This study will be conducted in accordance with the ethical principles that have their origin in the Declaration of Helsinki as stated in 21 CFR §312.120(c)(4); consistent with good clinical practice and all applicable regulatory requirements.

Before initiating this trial, the Investigator will have written and dated approval from the Institutional Review Board for the protocol, written informed consent form, subject recruitment materials, and any other written information to be provided to subjects before any protocol related procedures are performed on any subjects.

The clinical investigation will not begin until all approvals have been secured.

8.2 INSTITUTIONAL REVIEW BOARD APPROVAL

The protocol, the proposed informed consent form, and all forms of participant information related to the study (e.g. advertisements used to recruit participants) will be reviewed and approved by the UCSF CHR (UCSF Institutional Review Board). The initial protocol and all protocol amendments must be approved by the IRB prior to implementation.

8.3 INFORMED CONSENT

All participants must be provided a consent form describing the study with sufficient information for each participant to make an informed decision regarding their participation.

8.4 CHANGES IN PROTOCOL

Once the protocol has been approved by the UCSF IRB, any changes to the protocol must be documented in the form of an amendment. The amendment must be signed by the Investigator and approved by the CHR prior to implementation.

If it becomes necessary to alter the protocol to eliminate an immediate hazard to patients, an amendment may be implemented prior to IRB approval. In this circumstance, however, the Investigator must then notify the IRB in writing within five (5) working days after implementation.

9 PROTECTION OF HUMAN SUBJECTS

9.1 PROTECTION AGAINST RISKS

All subjects will be under close medical supervision of the CRS staff and study doctor. Furthermore, all study procedures will be subject to the approval of UCSF IRB. Patient confidentiality will be maintained as carefully as possible. Authorization for disclosure of protected health information for research purposes will be required in accordance with HIPPA regulations. Patients will be informed that all efforts will be made to keep personal information confidential, however, absolute confidentiality cannot be guaranteed. Patients will be informed that their

protected health information may be disclosed if required by law. All of this will be presented in the informed consent document and authorization for disclosure form.

APPENDIX A: DATABASE GUIDE

Screening Visit

1. Screening Log

The Screening Log is a list of all participants who came into the 20th street Tobacco Research Center or ZSFG location for a screening visit for the V-PAX study. This log details information about each participant as well as the outcome of the visit. Specifically, the Screening Log contains the following information: participant's name, date of screening visit, RedCap ID from the RedCap pre-screening email survey, study ID number, toxicology and pregnancy screening results, eligibility status and reason, ethnicity, race, sex, 5B status (including whether or not the participant was a no-show) and 5B start and end date.

- Location: t-Drive
- Folder: 7845 V-PAX
- Sub-folder 1: Databases
- Subfolder 2: Logs
- name: V-PAX Screening Log
- Password: 7845THC

2. Saliva Cotinine Screening Log

The Saliva Screening Log is a list of the cotinine values for participants who came in for a V-PAX screening visit.

- Location: s-Drive
- Folder: Clinical Research
- Sub-folder 1: Screening Log
- Subfolder 2: 7845 V-PAX
- name "7845 V-PAX Saliva Cotinine Screening Log"

3. Eligible Participant's Log (only participants deemed eligible at screening)

The Eligible Participant's Log is a list of all participants deemed eligible to participate in the Crossover study after their screening visit. This log contains the following information: participant's name, study ID, product assignment number, starting product, MRN number, 5B admission and discharge date, and notes regarding withdrawals, no-shows and early discharges. Overall, we had 54 eligible participants, and 36 completed participants.

- Location: t-Drive
- Folder: 7845 V-PAX
- Sub-folder 1: Databases
- Subfolder 2: Logs
- name: V-PAX Screening Log
- Password: 7845THC

4. V-PAX Database

The data collected at the screening visit is located on RedCap under the project titled V-PAX Study Database. This project includes the following forms: Participant Summary Form, Screening Eligibility Checklist, demographic information, Physiological Assessment, protocol violation, con meds, and adverse events.

Location: https://redcap.ucsf.edu/redcap_v9.1.13/index.php?pid=21357

5. V-PAX study participant survey Database

The data collected at the screening visit and study visits 1-3 is located on RedCap under the project titled V-PAX study participant survey Database. This project includes the following forms: demographic information, screening packet, SDS, THC Use history questionnaire, NDSS, PS-ECDI, E-WISDOM, E-FTND, CES-D, MNWS, M-CES, PANAS, DEQ-5, MCQ-SF, M-SCALE, VAS.

- Location: https://redcap.ucsf.edu/redcap_v9.1.13/index.php?pid=24277

1. Crossover Specimen Log

The Crossover Specimen Log is a file in a database used to track all of the specimens collected during participants' orientation visit and inpatient study days. This log contains the following information: specimen type, dates and times of specimen collection, date of lab sample transfers, and volume/pH of urine specimens.

- a. Location: t-Drive
- b. Folder: 7845 V-PAX
- c. Sub-folder 1: Databases
- d. Subfolder 2: Logs
- e. name: 7845-V-PAX specimen Log

2. Urine Catecholamine Summary

The plasma Catecholamine Summary contains the catecholamine data from participants 7845-002-7845-018, including: norepinephrine, epinephrine, and dopamine per volume.

- Location: t-Drive
- Location: t-Drive
- Folder: 7845 V-PAX
- Sub-folder 1: Databases
- Subfolder 2: Logs
- name: 7845-V-PAX specimen Log
- Information is downloaded from ARUP Labs via email from program manager
